Patients will be screened by a member of the research team. Patients will be adults (men and women) who have been identified by a provider as having pre-diabetes (A1c 5.7-6.4) or diabetes (A1c 6.5 or above) and: 1.) Enter one of the two diabetes programs during the study; 2.) Self-identify as “Latino;” 3.) Can identify a social support or key member of their social network who will agree to participate with them; 4.) Are not pregnant (participants who become pregnant during the study will be excluded); and 5.) Have household income 250% of the FPL or below. Participants who become pregnant during the study will be excluded. Additionally, we have discovered that there is a difference between the A1c test that CTSC runs and the test run at Quest or TriCore. The test CTSC uses is reliably .2 lower and this is cited in the literature. Therefore, it is appropriate for us to enroll individuals who have a test at another lab that shows them to be pre-diabetic (A1c 5.7-6.4) even if our baseline lab comes back lower (5.5-6.2). However, any individual whose blood gathered by our data collectors at baseline returns with an A1c below 5.5 will be disenrolled.

Social supports will be adult individuals who are identified by the patient participants and who agree to participate.

Advisory Board Members will be seven members of our Project Patient Advisory Board.

PROTOCOL TITLE: Comparing Program Options for Latinos with Diabetes

3.3 Indicate specifically whether you will include or exclude each of the following special populations: (You may not include members of the above populations as subjects in your research unless you indicate this in your inclusion criteria.)

1. *Adults unable to consent*
2. *Individuals who are not yet adults (infants, children, teenagers)*
3. *Pregnant women*
4. *Prisoners*

We will not recruit:

- Adults unable to consent
- Individuals who are not yet adults (infants, children, teenagers)
- Prisoners
- Pregnant women.

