7.0 Study Timelines*

7.1 *Describe:*

1. *The duration of an individual subject's participation in the study.*

Each year up to 12 staff or provider participants (6 per site) will be enrolled to do one 2-hour interview.

PROTOCOL TITLE: Comparing Program Options for Latinos with Diabetes

Each patient and social support participant will be enrolled for 12 months. We will gather data at baseline, 3 months, 6 months and 12 months. Data collection appointments will last approximately 1 hour. A subset of patient and social support participants will be invited to do an interview or a focus group. Interviews and focus groups will last approximately 1-2 hours.

Seven Patient Advisory Board members will be asked to participate in a series of interviews between June 1, 2017 and August 4, 2017. Interviews will last 1-3 hours.

2. *The duration anticipated to enroll all study subjects.*

Enrollment will begin in month 3 of the study.

Enrollment will end in month 22.

Data collection will end in month 34.

3. *The estimated date for the investigators to complete this study (complete primary analyses)*

This study is a 3-year project. It is slated to end in month 36. The study was funded to begin November 1, 2016 and the official end date is October 31, 2019. We anticipate continuing to analyze data for six months to one year following the official end of the project.

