Eligibility Screening: potential participants who agree to being screened for eligibility will be contacted by a member of the research team and asked the eligibility screening questions, including requesting information about a potential social support partner. The patient participant will be offered the opportunity to contact their potential social support partner to inform him or her that a research team member will be in contact to conduct an eligibility screening. When the patient partner gives permission to contact the potential social support partner, a member of the research team will contact the potential social support partner and conduct the eligibility screening. If both the patient participant and his or her social support partner are deemed eligible, baseline data collection appointments will be scheduled with both participants. The information collected during the eligibility screening will be hand-written on an Eligibility Screening form and given to the Patient Engagement Coordinator, who will enter it into REDCap in the Eligibility Screening project. The Patient Engagement Coordinator will then create a record for the participant in the PCORI Diabetes Project in REDCap and assign a participant ID (PID) to the participant. The Patient Engagement Coordinator will keep a master list of the participants' names and PIDs both electronically and in hard copy. The electronic copy will be saved on her password-protected laptop, which is stored in a locked cabinet at One Hope when not in use. The hard copy will also be stored in a locked cabinet at One Hope.

Data Collection: at the baseline data collection appointment, the PDCS will collect and enter contact and demographic information into separate data collection instruments in the PCORI Diabetes Project in REDCap. At the baseline and all three follow-up appointments, the PDCSs will also administer the survey instrument to the participants, responses to which will be entered into a third data collection instrument in the same project. The PDCSs will also collect BMI measurements (weight and height) and draw blood for A1c testing at the baseline and all follow-up appointments and will collect a hair sample at the baseline and six-month follow-up appointment. The BMI measurements will be entered into a fourth data collection instrument in the PCORI Diabetes Project by the PDCS during

PROTOCOL TITLE: Comparing Program Options for Latinos with Diabetes

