A1c: The PDCSs will be trained in phlebotomy. The PDCS will draw blood samples at the same time they administer the survey. The UNM Clinical and Translational Science Center (CTSC) Clinical Research Laboratory will provide the collection kits for specimen collection. Blood will be drawn, labeled and stored using standard phlebotomy protocols, and the *Patient Engagement Coordinator* will deliver specimens to the CTSC lab where they will be tested on whole blood following the lab's "*Hemoglobin A1c*" procedure using the DCA Vantage 2000 analyzer⁹¹. After testing, specimens will be disposed of according to CTSC lab protocol. For A1c (>10), we will notify the participant's PCP. If we see a lab value that could indicate an emergency (Glucose > 400 mg/dl, < 60 mg/dl), we will contact the participant to make sure they are aware of their A1c status and that they are receiving appropriate care. For women with an elevated A1c, when we contact them to tell them about their elevated test results we will inquire again whether or not they are or think they might be pregnant. If so, Co-Investigator [name] will provide them with a referral to UNM's High Risk Obstetrics Clinic. Additionally, we have discovered that there is a difference between the A1c test that CTSC runs and the test run at Quest or TriCore. The test CTSC uses is reliably .2 lower and this is cited in the literature. Therefore, it is appropriate for us to enroll individuals who have a test at another lab that shows them to be pre-diabetic (A1c 5.7-6.4) even if our baseline lab comes back lower (5.5-6.2). However, any individual whose blood gathered by our data collectors at baseline returns with an A1c below 5.5 will be disenrolled.

Body Mass Index (BMI): The PDCS will document patient participant height and weight and calculate his or her BMI. Height and weight measurements will be taken using a standardized protocol. Height measurements will be collected using SHORR boards against

PROTOCOL TITLE: Comparing Program Options for Latinos with Diabetes

flat walls on level, firm (not carpeted) flooring. Weight measurements will be collected using calibrated, research-grade SECO scales. Two measurements will be taken for height and two for weight for each participant at each data collection point. An average of the two measures of height and an average of the two measures of weight will be used in the BMI calculation.

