- 1.) Hypothesis: The CCM model will result in a larger decrease in percent A1c from baseline to 6 months with Cohen's f ES = 0.06 as compared to the DSMS. Previously published studies and institutional experience evaluating culturally competent diabetes management programs report changes in percent A1c with effect sizes of 0.01 to 0.06 in studies ranging in sample size per arm from 26 to 133.^{66,105-107}
- 2.) Hypothesis: The CCM model will result in a larger decrease in BMI from baseline to 6 months than DSMS with a clinically meaningful difference of 1.5 kg/m² between the groups (Cohen's f ES = 0.06).^{67,68}
- 3.) Hypothesis: Compared to DSMS, CCM will result in a larger decrease (by 3 points) in PHQ-9 scores from baseline to 6 months (Cohen's f ES = 0.06).¹⁰⁷⁻¹⁰⁹

Note: It is coincidental that the effect sizes (and power) are the same for each of the three secondary outcomes

Power Calculations. We will recruit N=240 patient-social support pairs (n=120 per site) with anticipated 20% attrition to obtain complete data on at least n=96 per site. Comparing response changes on the DKQ, PAM-13, and DHQ-9 from baseline to 6 months between the CCM to the DSMS, the two-sided Type I error rate was adjusted for the number of comparisons made (four comparisons for the co-primary outcomes) using a Bonferroni correction ($\alpha=0.0125$). The power analyses for detecting site differences among change scores were based on multiple linear regression models including demographic characteristics, participants' perceived cultural competence of providers (CAHPS-CC), and social supports' change scores on the DHQ, PAM-13, and DHQ-9 as covariates. We report Cohen's f effect sizes based on the regression method.^{110,111}

The power for the primary endpoints with n=96 per site and $\alpha=0.025$ are as follows:

- 1.) Change in DKQ summed score: $\Delta_{CCM-DSCS} = 2.2$ (SD = 3.8), power = 96%, Cohen's f effect size (ES) = 0.09
- 2.) Change in PAM-13 raw score: $\Delta_{CCM-DSCS} = 12.7$ (SD = 24.8), power = 85%, Cohen's f ES = 0.07

The power for the secondary endpoints with n=96 per site and $\alpha=0.017$ for comparing the CCM to the DSMS:

- 1.) Change in A1c: $\Delta_{CCM-DSCS} = -0.5$ (SD = 1.0), power = 84%, Cohen's f ES=0.06.
- 2.) Change in BMI: $\Delta_{CCM-DSCS} = -1.5$ (SD = 3), power = 84%, Cohen's f ES=0.06.
- 3.) Change in depression scores (PHQ-9): $\Delta_{CCM-DSCS} = -3$ (SD = 6), power = 84% Cohen's f ES = 0.06.

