1.) **A1c:** For patients from CDE-UNMH, we will obtain baseline A1c results from the CDE program files. For One Hope patients, the PDCS who will be trained in phlebotomy will draw blood samples at the same time they administer the baseline survey. For patients from both sites, the PDS will draw blood samples at the 3-month, 6-month and 12-month data collection sessions. Blood will be drawn, labeled and stored using standard phlebotomy protocols, and the *Patient Engagement Coordinator* will deliver specimens to the CTSC lab where they will be tested for A1c.

2.) **Body Mass Index (BMI):** The PDCS will document patient height and weight and calculate his or her BMI. Height and weight

PROTOCOL TITLE: Comparing Program Options for Latinos with Diabetes

measurements for all participants will be taken using a standardized protocol. Height measurements will be collected using SHORR boards against flat walls on level, firm (not carpeted) flooring. Weight measurements will be collected using calibrated, research-grade SECO scales. Two measurements will be taken for height and two for weight for each participant at each data collection point. An average of the two measures of height and an average of the two measures of weight will be used in the BMI calculation.

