19.0 Setting

19.1 *Describe the sites or locations where your research team will conduct the research.*

1. *Identify where your research team will identify and recruit potential subjects*

The purpose of the data collected through this project is to investigate the comparative effectiveness of two evidence-based models for creating program cultural competency in diabetes self-management programming. We will compare two diabetes self-management programs that serve a large low-income Latino population and that employ different evidence-based models of culturally competent health promotion. We will gather data from participants at One Hope Centro de Vida Health Center in Albuquerque's International District and the Center for Diabetes Education at the University of New Mexico Hospital located on [name].

2. *Identify where research procedures will be performed.*

Most One Hope data collection will occur on the premises of One Hope, although if participants would like to have an appointment off-site at a location of their convenience, that will be possible.

Data collection from participants at CDE UNMH will occur at the facilities of CDE UNMH or at a location of convenience to the participant.

Interviews will be conducted at a location of convenience to the participant.

PROTOCOL TITLE: Comparing Program Options for Latinos with Diabetes

Focus Groups will be held at the facilities of One Hope.

Blood analysis will be conducted at the CTSC lab.

Analysis of hair samples will be conducted in the UNM lab of Co-I [name] in Department of Pathology, on the UNM-HSC campus, [name].

3. *Describe the composition and involvement of any community advisory board.*

We created a Project Patient Advisory Board involving patient partners. The 11-member Patient Advisory Board will meet quarterly to provide guidance and oversight for the research. The Advisory Board consists of 4 Latino diabetes patients and 3 caregivers for people with diabetes, plus the PIs, the Patient Engagement Coordinator, and [name]. We formed this board with support from 2 PCORI Tier Awards and members of the board met once a month over a two year period to plan this research. The patient and caregiver members identified the research question and the measures for this study.

4. *For research conducted outside of the organization and its affiliates describe:*

N/A

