Data Collection: at the baseline data collection appointment, the PDCS will collect and enter contact and demographic information into separate data collection instruments in the PCORI Diabetes Project in REDCap. At the baseline and all three follow-up appointments, the PDCSs will also administer the survey instrument to the participants, responses to which will be entered into a third data collection instrument in the same project. The PDCSs will also collect BMI measurements (weight and height) and draw blood for A1c testing at the baseline and all follow-up appointments and will collect a hair sample at the baseline and six-month follow-up appointment. The BMI measurements will be entered into a fourth data collection instrument in the PCORI Diabetes Project by the PDCS during each appointment. The A1c results will be entered into a fifth data collection instrument and the hair cortisol results entered into a sixth in the same project by the Data Manager when the results are provided to her.

The contact and demographic information data collection instruments are the only data collection instruments in the PCORI Diabetes Project that contain personally identifying information. The data collection instruments that contain the participant's survey responses and biological

PROTOCOL TITLE: Comparing Program Options for Latinos with Diabetes

measures do not contain any personally identifying information. Each participant's data is linked across the six data collection instruments in the PCORI Diabetes Project by his or her unique Study ID, which is automatically generated by REDCap when the Patient Engagement Coordinator generates the record.

In sum, there will be three separate projects in REDCap: the Pre-Screening project, the Eligibility Screening project, and the PCORI Diabetes Project, which contains the participant contact information, demographic information, survey responses, BMI measurements, A1c results, and hair cortisol results in six separate data collection instruments. The PID that is generated before the baseline data collection appointment will be retroactively added to the relevant record in both the Pre-Screening and Eligibility Screening projects by the Research Manager or the Data Manager to allow for tracking of recruitment, enrollment, and attrition. This will be the only link across the three projects.

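### BMI is recomputed from a newly measured height at every visit, which adds small but avoidable noise to the BMI-change endpoint in adults

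*Combined protocol and SAP*

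**What the plan says.** The BMI rule appears twice in the combined protocol and SAP, in section 9.2 (Physical Measures) and section 11.5 (item 1.v), with the same content. On readings: "Two measurements will be taken for height and two for weight for each participant at each data collection point". On the calculation: "An average of the two measures of height and an average of the two measures of weight will be used in the BMI calculation".

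The data-collection text in section 9.2 confirms the schedule: "The PDCSs will also collect BMI measurements (weight and height) and draw blood for A1c testing at the baseline and all follow-up appointments". Section 25.3 adds: "The BMI measurements will be entered into a fourth data collection instrument in the PCORI Diabetes Project by the PDCS during each appointment". No section carries the baseline height forward or pools heights across visits.

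The BMI paragraphs also contain safeguards: a standardized procedure, SHORR boards against a flat wall on level, uncarpeted flooring, and calibrated scales. Section 19.1 allows measurement away from the program premises. For One Hope it says "if participants would like to have an appointment off-site at a location of their convenience, that will be possible", and there is a comparable allowance for CDE-UNMH.

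Section 3.2 restricts patients to adults. Section 7.1 gives the follow-up: "Each patient and social support participant will be enrolled for 12 months". Section 11.2 makes BMI change from baseline to 6 months a secondary endpoint with a "clinically meaningful difference of 1.5 kg/m² between the groups". It plans on an SD of 3, 96 patients per site, alpha 0.017 and power of 84%.

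**The concern.** Adult height is effectively constant over 12 months, so a between-visit difference in recorded height reflects posture, board set-up, collector or keying rather than the program. BMI divides by height squared, so a relative error in height becomes twice that relative error in BMI. If each visit's BMI uses its own height, the errors at baseline and at 6 months both enter the change score. Averaging two readings within a visit reduces independent reading error, but not error that both readings share.

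Two things could be at stake. The first is precision: extra variance in BMI change. The second is bias in the site comparison, but only if height error moves between visits by a different amount at the two sites.

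**Working it through.** **1. The rule as written.** Two readings at each of four visits make eight heights per participant. A rule that averages the two measures therefore points to the pair from that visit. The text does not say outright that each visit's BMI uses that visit's height, but this is its natural reading, and no other rule is given.

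**2. The plan's power.** Inputs from section 11.2: difference 1.5, SD 3, n = 96 per site, alpha 0.017. Two-sided testing is stated there for other outcomes and is taken to apply here.

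- Standard error = 3 × √(2/96) = 0.433.
- 1.5 / 0.433 = 3.464. The critical value is 2.387.
- Power = Φ(3.464 − 2.387) = Φ(1.077) = 85.9%. A noncentral t calculation with 190 df gives 85.4%.

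Both are within 2 points of the stated 84%, so the plan's figure reproduces.

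**3. From height error to BMI change.** The documents give no mean height, mean BMI or height error. Assume height H = 160 cm and BMI 32.

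- Effect of a height error d: about 2 × BMI × d / H. For 1 cm this is 2 × 32 × 1 / 160 = 0.40 kg/m².
- Noise SD in the change between two visits, with visit-level error SD s independent across visits: √2 × 2 × 32 × s / 160 = 0.566 × s.
- SD of change if the planned SD of 3 excludes this noise: √(9 + noise²).

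| Visit-level height error SD | Noise SD in BMI change | Share of planned variance (9) | SD of change | Power |
|---|---|---|---|---|
| none | 0 | 0 | 3.00 | 85.9% |
| 0.5 cm | 0.28 | 0.9% | 3.01 | 85.6% |
| 1.0 cm | 0.57 | 3.6% | 3.05 | 84.6% |
| 1.5 cm | 0.85 | 8.0% | 3.12 | 82.8% |

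The last row as an example: noise² = 0.72, SD = √9.72 = 3.118, and 1.5 / (3.118 × 0.1443) = 3.333. Power = Φ(3.333 − 2.387) = 82.8%.

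**4. More favourable case.** If the two readings at a visit have fully independent errors, averaging divides the visit-level SD by √2. Single-reading SDs of 0.5 and 1.0 cm then give noise SDs of 0.20 and 0.40 kg/m² and power of 85.8% and 85.3%. The loss is at most about 0.7 points.

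**5. If the planned SD of 3 already includes height error.** There is then no loss against plan, and a fixed height would be a small gain. Removing noise SDs of 0.28 and 0.57 brings the SD to 2.99 and 2.95, and power to 86.3% and 87.3%.

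**6. Bias.** An offset that is the same at every visit at a site largely cancels within each participant. A shift between visits at one site only does not. A hypothetical 0.5 cm shift gives 2 × 32 × 0.5 / 160 = 0.20 kg/m², and 0.20 / 1.5 = 13% of the target.

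**7. What remains with one fixed height.** The additive error drops out of the change. A fixed height that is wrong by 0.5 cm only rescales the change by about 2 × 0.5 / 160 = 0.6%.

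**The case against.** The strongest reply is that the plan already controls height measurement and that what is left hardly matters. The board, wall and floor requirements carry no off-site exemption, so permission to meet elsewhere does not relax them. Two readings per visit can expose a discordant entry, although no tolerance is stated, and section 11.4 provides quality checks on the entered data. On these figures power falls below the stated 84% only at a visit-level error SD of 1.5 cm, and then by about 1 point. Every height-error SD is an assumption. All of this stands, and it limits the importance of the point. It does not answer the error common to both readings at a visit, and section 11.4 describes no comparison of heights across visits.

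Two stronger readings are tempting and should not be drawn.

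- A reader might infer that gross height errors could swamp the effect sought, because a 5 cm error moves one person's BMI by about 2.0 kg/m² (2 × 32 × 5 / 160), more than 1.5. That compares an individual value with a difference between group means. One such error among 96 patients moves a site mean by 2.0 / 96 = 0.02 kg/m², or 1.4% of the target.
- A reader might infer that any difference in how the two sites measure height biases the comparison. A constant offset largely cancels in the change. Bias needs drift that differs by site, and nothing in the documents indicates that this occurs.

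**Conclusion.** The point holds as a minor, nearly free improvement to one of three secondary endpoints. As written, the plan lets visit-to-visit height error into BMI change when a single height per adult would keep almost all of it out. With height 160 cm, BMI 32 and visit-level error SDs of 0.5 to 1.5 cm, this error equals 0.9% to 8.0% of the planned variance. It costs about 0.3 to 3.1 points of power if the planned SD of 3 excludes it, and nothing against plan if that SD includes it. The documents do not settle which applies.

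This does not support a claim that the sample size is inadequate or that the BMI comparison is biased. Confidence is high for the mechanism. The size rests on assumed inputs, and the drift figure is hypothetical.

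**What to change.** In the BMI paragraphs of sections 9.2 and 11.5, state that for analysis BMI at every visit is derived from that visit's mean weight and one fixed height per participant, namely the mean of all that participant's valid height readings. Say in advance how a discordant reading is queried and when it counts as invalid, without reference to site or outcome.

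Keep measuring height at follow-up. Dropping those readings would remove the check on a wrong baseline height, which a fixed-height rule would otherwise carry into every visit. The BMI that the data collector calculates at the appointment can stand as provisional.

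The only cost is that the analysis BMI is derived at the analysis stage, because the mean of all readings is known only after the last visit. No new data or visits are needed, and the rule can be applied to data already collected.
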